Randomized multi-center trials have shown that basal bolus treatment with glargine U100 improve glycemic control and reduce the rate of hospital complications compared to sliding scale regular insulin (SSI) (12-14). In general surgery patients, the basal bolus approach results in significant reduction in a composite of hospital complications including postoperative wound infection, pneumonia, bacteremia, and acute renal and respiratory failure (15). The hospital hypoglycemia rate was reported in 3% in medicine (16) and 12% in surgery (17) patients treated with basal bolus regimen. Based on these results, clinical practice guidelines have recommended the use of basal bolus approach as the preferred insulin regimen for the management of non-ICU patients with diabetes (18-20).

The Food and Drug Administration and the European Commission recently approved Glargine U300 insulin for the treatment of patients with diabetes. Glargine U300 is long-acting insulin with duration of action longer than 24 hours (21, 22). The results of the Edition clinical trials with more than 3500 patients demonstrated that glargine U300 resulted in similar improvement in glycemic control and with a lower rate of nocturnal hypoglycemia compared to glargine U100 (23-27). The efficacy and safety of glargine U300 has been documented in patients with type 1 and type 2 diabetes (22-27); however, no previous studies have assessed the safety and efficacy of these new formulations in the inpatient (hospital) setting. In addition, certain features of glargine U300 needs to be investigated in the hospital including 1) prolonged duration of action, which may limit the ability to make day-to-day adjustments in insulin dosage; 2) a steady-state insulin concentration achieved after second or third day of therapy; and limited safety data in acutely ill patients with altered nutritional status. Accordingly, the present randomized clinical trial will compare the efficacy and safety of a basal bolus regimen with glargine U300 and glargine U100 (standard of care) in general medicine and surgery patients with T2D.

B. Specific Aims:

Aim 1. To determine differences in inpatient glycemic control, as measured by mean daily blood glucose concentration and frequency of hypoglycemia, in general medicine and surgery patients with T2D treated with basal bolus regimen with glargine U300 and U100 plus glulisine insulin before meals.

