The primary outcome of the study is to determine differences in glycemic control as measured by mean daily blood glucose concentration between treatment groups. For each subject, we will take the average of all pre-meal and bedtime glucose values collected after the first day of therapy during the hospital stay (up to 10 days).

Secondary outcomes include differences between treatment groups in any of the following measures:

1. Differences in mean daily glucose in patients admitted to medicine and surgery services.
2. Differences in mean daily glucose in patients with admission HbA1c lower than and higher than 8%.
3. Differences in mean daily glucose in patients with length of stay shorter and longer than 3 and 5 days.
4. Proportion of BG readings within target of 80 mg/dl and 180 mg/dl before meals.
5. Number of BG readings between 80 mg/dl and 180 mg/dl before meals without hypoglycemia.
6. Number of patients with hypoglycemia (defined as a BG < 70 mg/dl) and number of events adjusted by length of stay (event rate).
7. Number of patients with severe hypoglycemia (defined as a BG < 40 mg/dl) and number of events adjusted by length of stay (event rate).
8. Length of hospital stay.
9. Cardiac complications are defined as myocardial infarction, cardiac arrhythmia requiring medical treatment, or cardiac arrest.
10. Acute renal failure defined as a clinical diagnosis with documented new-onset abnormal renal function (increment in serum creatinine > 0.5 mg/dL from baseline).
11. Hospital mortality.

IV.d. Plan. This study will include male or female subjects > 18 years. Due to the design of this study, there will be no run-in period. Upon arrival to the emergency department or medical or general surgical wards, subjects will be screened. Patients with a known history of T2D treated with diet alone, any combination of OADs, and insulin prior to admission will be considered potential candidates for this study. Patients treated with degludec, glargine U300 or with long-acting GLP1-RA (dulaglutide, albiglutide and weekly exenatide) prior to admission will be excluded. Patients admitted with acute or chronic medical illnesses, emergency or elective surgical procedures and trauma would be included in the study. The goal of insulin therapy is to maintain fasting and pre-meal blood glucose levels between 80 mg/dl and 180 mg/dL while avoiding hypoglycemia.

A total of 180 patients with T2D with a blood glucose > 140 mg/dL and < 400 mg/dL will be randomized to receive:

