- If a patient develops hypoglycemia (BG <70 mg/dL), the insulin TDD (basal and prandial) should be decreased by 20%.
- If a patient develops severe hypoglycemia (BG <40 mg/dL), the insulin TDD (basal and prandial) should be decreased by 30-40%.

IV.g. Data Analysis:

Aim 1. To determine differences in inpatient glycemic control, as measured by mean daily blood glucose concentration and frequency of hypoglycemia, in general medicine and surgery patients with T2D treated with basal bolus regimen with glargine U300 and U100 plus glulisine insulin before meals.

Due to the lack of efficacy and safety data with the use of glargine U300 in the inpatient setting, periodic conduct interim analyses will be conducted every 6 months to monitor the primary outcome and rate of hypoglycemia, and to modify the study design regarding interval of administration and dosage adjustment for basal insulin (see page 9, Data Safety Monitoring Plan, sections IV. f. and IV.g.).

Sample Size and Power Calculations:

The primary endpoint in this study is glycemic control measured by mean daily BG concentration. To show the non-inferiority of glargine U300 and U100 in terms of glycemic control, we set the equivalence margin as 18 mg/dl (1 mosm/l), from a view that a difference <18 mg/dl is usually not considered as clinically significant (12, 14, 16). Based on the results from Rabbit medicine and surgery trials, it is reasonable to assume the standard deviation of mean daily BG is bounded above by 45 mg/dl. Assuming the true BG difference between the treatment groups is zero, and using one-sided, two-sample t-tests, we require 78 subjects for each treatment group to achieve 80% power. Accounting for 10% attrition rate, we would need 90 patients per treatment group, which means 180 subjects in total, to achieve >80% power in Aim 1.

Analysis of Primary Endpoint:

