The primary endpoint for Aim 1 is glycemic control measured by mean daily BG concentration among the two study groups. Blood glucose will be measured before each meal and at bedtime. We will first perform cross-sectional analyses using nonparametric Krustal-Wallis tests (or Wilcoxon tests) or one-way ANOVA, followed by repeated measures ANOVA to estimate and test the difference between the two treatment groups while simultaneously examining mean daily BG across multiple days during treatment. A mixed effect model may be used to further account center effect or other potential confounders for the BG outcome. Stepwise, backward, or forward model selection strategy will be adopted to determine the variables to be included in the final model. Standard diagnostic and model checking procedures will be applied to examine the fit of the developed models.

Analysis of Secondary Endpoints:

Secondary endpoints for Aim 1 in this study include incidence of hypoglycemia, number of hypoglycemic

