events, number of severe hyperglycemia, mean daily fasting BG, daily insulin dose, length of hospital stay, acute renal failure and hospital mortality. Blood glucose will be measured before each meal and at bedtime. For discrete outcomes (such as hypoglycemia outcomes), if the outcome is binary (e.g. with or without hypoglycemia), we will first conduct nonparametric comparisons based on a two-sided Chi-square test (or Fisher's exact test in the presence of low incidence rates), followed by the Cochran-Mantel-Haenszel test, which adjusts for the potential center effect. If the discrete outcome is a count outcome (such as the number of hypoglycemic event), we will perform Poisson regression (or Negative Binomial regression) that adjusts for the length of hospital stay to assess the difference in the count outcome between the treatment groups. We also value the repeated measures analyses based on mixed effect models. This is because they will allow us to assess treatment effect fine tuned according to other confounders of the BG outcomes. By these considerations, we will conduct both types of analyses to provide a thorough evaluation of the hypothesis of interest. For continuous outcomes that are not repeated measures (such as length of hospital stay), we will use two-sample t-tests or nonparametric Wilcoxon tests to compare them between groups. Transformations will be applied if normality violation is detected. Multivariate linear regression will be further conducted to assess the difference in continuous secondary outcomes between the two groups while other relevant covariates. We will use standard model selection and model checking procedures for linear regression to decide the final models and assess their fits to the data.

IV.f. Data and Safety Monitoring Board (DSMB):

The Data and Safety Monitoring Board (DSMB) will review unblended data on safety, treatment compliance, and evaluate the efficacy of the intervention being studied in this clinical trial. The DSMB will meet at 6-month intervals and report on study progress to the IRB.

IV.g. Interim Analysis and Stopping Rules: We plan to perform one interim analysis on the primary endpoint every 6 months and when half of the subjects have been randomized. The trial will be stopped if there is evidence beyond a reasonable doubt of a difference in the rate of death and hospital complications (two-sided alpha level, <0.01) between the treatment groups.

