Subjects with persistent hyperglycemia (≥ 2 glucose readings ≥ 400 mg/dL, ≥ 3 consecutive glucose readings > 280 mg/dL, or with a mean daily blood glucose concentration ≥ 280 mg/dL) and no treatable intercurrent cause for the hyperglycemia has been identified, will be considered as treatment failure and discontinued from the study. If needed, subjects will be started on continuous insulin infusion.

VII. Study Sites: This study will be performed at Grady Memorial Hospital, Emory University Hospitals, Atlanta, GA, Minneapolis Medical Research Foundation-Hennepin Medical Center, Minneapolis, and The Cleveland Clinic Foundation, Ohio.

VIII. CLINICAL MANAGEMENT GUIDELINES

VIII.a. Admission Laboratory Studies

Standard of care laboratory studies including glucose, HbA1C, and chemistry will be measured on admission and as determined by the treating physician.

For **research purposes** a blood sample will be obtained to measure HbA1C at 1 month and 3 months after discharge. In addition, a urine pregnancy test will be performed, when clinically indicated prior to randomization (in female subjects of child bearing potential only).

VIII.b. Assessment and Monitoring of Hospital Mortality

The investigators and research team will follow study subjects daily and the presumed cause of death will be recorded. Information on the attending physician’s summary of events surrounding subject’s demise will also be documented.

VIII.c. Assessment and Monitoring of Nosocomial Infections

Nosocomial infections will be diagnosed based on standardized CDC criteria (40). New nosocomial infections will not be diagnosed until 48 hours after study initiation to minimize the chance that the infection was actually present (but undiagnosed) prior to study initiation.

The investigators will review each subject’s records regarding potential new infection diagnosis daily on each weekday from Monday to Friday. Data from the weekends will be collected on the following Monday. The coded infection diagnosis and the presumed causative microorganism will be determined daily on a Monday to Friday basis, with weekend data entered on the following Monday.

Aim 1. Inpatient Arm – Flow Chart

Visit Type	Hosp- Day 1	Hosp- Day 2	Hosp- Day 3	Hosp- Day 4	Hosp- Day 5	Hosp- Day 6	Hosp- Day 7	Hosp- Day 8	Hosp- Day 9	Hosp- Day 10
Visit #	1	2	3	4	5	6	7	8	9	10
Time-days	1	2	3	4	5	6	7	8	9	10
Inf. consent	x									
Inclusion/excl criteria	x									
Randomization	x									

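### Treatment failures leave the study, not just the insulin regimen: a day-1 failure has no primary value, a later one a truncated value, and the net bias is unknown

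*Combined protocol and SAP*

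**What the plan says.** **Failure rule.** Treatment Failure Criteria, placed after the withdrawal criteria in VI.d, applies to "Subjects with persistent hyperglycemia (≥ 2 glucose readings ≥ 400 mg/dL, ≥ 3 consecutive glucose readings > 280 mg/dL", or to a mean daily glucose of at least 280 mg/dl, when no treatable intercurrent cause is found. Such a patient "will be considered as treatment failure and discontinued from the study. If needed, subjects will be started on continuous insulin infusion". No minimum time on therapy is required. VI.d item 3 separately withdraws a patient who goes to the ICU and needs continuous intravenous insulin.

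**Primary outcome.** IV.c takes, for each subject, the "average of all pre-meal and bedtime glucose values collected after the first day of therapy during the hospital stay (up to 10 days".

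**Analysis.** IV.g (Data Analysis) names no analysis population, no missing-data method and no handling of treatment failures. Failure is not among the IV.c outcomes. The IV.g secondary list includes "number of severe hyperglycemia, mean daily fasting BG, daily insulin dose, length of hospital stay, acute renal failure and hospital mortality", but not treatment failure.

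**Monitoring.** The six-monthly interim analyses look at the primary outcome and hypoglycemia, and may be used "to modify the study design regarding interval of administration and dosage adjustment for basal insulin". The trial stops on "evidence beyond a reasonable doubt of a difference in the rate of death and hospital complications".

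**The concern.** Patients are removed because their glucose is high, and glucose is the primary outcome. A patient who fails on day 1 leaves before any reading that counts has been taken. A patient who fails later keeps the high readings up to failure and loses the treated days after it. Neither value describes the patient's hospital stay, and IV.g does not say what to do with either.

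The introduction gives a reason to care about early failures on U300. Among the features it says need study in hospital is "a steady-state insulin concentration achieved after second or third day of therapy". If slow onset did cause early failures, those on day 1 would add nothing to the primary outcome, including at the interim looks that may change basal dosing. They would not be counted as failures either.

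**Working it through.** **1. Can a patient fail on day 1?** Yes, though it should be uncommon.
- Entry glucose may be anything above 140 and below 400 mg/dl (VI.b item 3), so a patient can start above the 280 threshold.
- On frequency, IV.g says "Blood glucose will be measured before each meal and at bedtime", which is four readings a day. Three consecutive readings above 280, or two at 400 or more, fit within the first 24 hours. If day 1 means the calendar day, three scheduled readings require randomization before lunch.
- The Aim 1 flow chart checks withdrawal criteria from day 1 but starts dose adjustment on day 2.
- Scaled starting doses, correction glulisine and the treatable-cause condition lower the risk without removing it.

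**2. The plan's sample size.** Margin 18, SD 45, true difference 0, 80% power (IV.g). Alpha is not stated. One-sided 5% gives n = 2(45/18)²(1.645 + 0.842)² = 77.3, so 78 per arm, as stated. One-sided 2.5% gives 99, which does not match. By the noncentral t distribution, power is 0.848 at 90 per arm, 0.813 at 81, 0.800 at 78 and 0.796 at 77. From 90, the planned 10% attrition leaves 81, and three more losses leave 78. Power is not the problem.

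**3. Unequal day-1 loss (illustration).** Assume U100 averages 145 mg/dl (the basal bolus mean in the preliminary surgery trial, III) and U300 averages 163 over all 90 patients, so the true difference equals the margin. Let U300 lose k more day-1 failures than U100, with mean X on the days not seen. The U300 mean then falls by s = k(X − 163)/(90 − k). The chance of a false claim is the power of the one-sided 5% test at a true difference of 18 − s, with 90 − k against 90 patients and SD 45.

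| k | X (mg/dl) | s (mg/dl) | False claim |
|---|---|---|---|
| 0 | – | 0 | 5.0% |
| 1 | 180 | 0.2 | 5.3% |
| 1 | 220 | 0.6 | 6.1% |
| 3 | 180 | 0.6 | 6.0% |
| 3 | 220 | 2.0 | 8.8% |

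For k = 3, X = 220: s = 3 × 57/87 = 1.97 and SE = 45√(1/87 + 1/90) = 6.77. The normal approximation Φ(−1.645 + 1.97/6.77) gives 8.8%. X = 280 with k = 3 would give 14.7%, but that describes a patient whose glucose stays at the failure level despite rescue. Equal loss in both arms gives a net bias near zero.

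**4. What k = 3 requires.** The simulation assumed four day-1 readings, between-patient SD 45, reading SD 30-45, and the two reading-count criteria only. Day-1 means of 200 (U100) and 220 (U300) give failure rates of about 2.3-2.4% and 5.3-5.5%, or 2.7-2.9 extra failures per 90. Adding the mean-daily criterion raises this to about 5-6. A 5 mg/dl day-1 difference, under the two criteria, gives about 0.5; three readings instead of four, at 200 v 220, give 2.0-2.4. The 20 mg/dl deficit is an assumption, and it exceeds the 18 mg/dl margin.

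**5. Truncated later failures (illustration).** Assume a day-2 failure averages 290 that day and then 160 for five days on rescue. The full average is (290 + 5 × 160)/6 = 181.7; the truncated value is 290. Three extra such patients on U300 move its mean by 3 × 108.3/90 = 3.6 mg/dl against U300. This is opposite in sign to step 3 and larger than its k = 3, X = 220 case.

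**6. What naive recovery would do.** Adding the post-rescue days for those three patients moves the difference 3.6 mg/dl back toward non-inferiority. If the difference using the 290 values were 18, the chance of a false claim would go from 5% to about 13%. Retaining patients therefore needs a second analysis that rescue cannot mask.

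**The case against.** The strongest objection concerns direction. A reader might infer that the rule tilts the trial toward non-inferiority of U300. The documents do not support that. It holds only for an excess of day-1 failures on U300, while truncated later failures count against their own arm. Slow attainment of steady state could produce failures on days 2 and 3 as readily as on day 1. The introduction raises it as something to investigate; it gives no glucose difference. Half the daily dose plus correction is glulisine in both arms. This objection stands, and step 5 confirms it.

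The second objection is that rescue glucose dilutes the primary comparison. It also stands (step 6) and shapes the fix.

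A third is that safety data are not simply lost. VIII.b has the team follow study subjects daily and record the presumed cause of death, XVI requires all serious adverse events to be transmitted, and the DSMB reviews safety and treatment compliance. A reader might infer that deaths and complications after failure go unrecorded; the text does not show that. What remains is that none of these provisions expressly covers a discontinued patient, although death and complications drive the stopping rule. Ward glucose readings probably also stay in the chart, but the plan does not say to extract or use them.

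**Conclusion.** The point holds as a gap in follow-up and analysis. As written, the failure rule leaves day-1 failures without a primary value, truncates the value of later failures, and leaves failure uncounted as an outcome. The missing data depend on the outcome, and no rule in IV.g repairs this.

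The net direction and size cannot be determined, because the documents give no failure rate and the two mechanisms oppose each other. For day-1 loss alone, 1 to 3 extra losses on U300 with unseen means of 180-220 mg/dl raise the false-claim chance at the margin from 5% to 5.3-8.8%. This rests on one-sided 5% alpha, SD 45, a true difference of 18 mg/dl and an assumed excess of failures on U300. The case for change rests on the low cost of the fix and the benefit of comparing all randomized patients, not on a demonstrated bias.

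**What to change.** 1. In Treatment Failure Criteria, replace discontinuation from the study with: *will stop the study insulin regimen but remain in the study; glucose, hypoglycemia, complications and death are recorded from the chart until discharge or day 10 and analysed in the assigned group.* Apply the same retention to VI.d item 3 (ICU with intravenous insulin), which could otherwise still remove the worst failures.
2. Add treatment failure to the IV.c secondary outcomes: number of patients and day of failure, by group.
3. In IV.g, report the primary comparison twice: with observed post-failure glucose, and with each day after failure set to 280 mg/dl. Claim non-inferiority only if it holds in both, because rescue insulin can mask a difference.
4. Leave the failure thresholds, the readings that count toward them and access to continuous infusion as they are, so that no safety trigger changes.

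The cost is the text edits, one added analysis and chart extraction for what should be a few patients. This assumes that ward glucose and hospital outcomes are charted in routine care. The downside is that post-failure glucose reflects rescue treatment, which is why both analyses are needed.
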